- As part of complex therapy to prevent complications and recurrence of chronic ENT organ diseases (including tonsillitis, otitis, sinusitis);
- As part of complex therapy for acute and chronic allergic diseases (including pollinosis, allergic rhinitis) complicated by a bacterial, viral or fungal infection;
- For preoperative preparation of patients before surgical interventions on ENT organs, and also during postoperative period to prevent infectious complications and relapses of the disease.
- As part of complex therapy to enhance the regenerative processes of ENT organ mucosae after acute viral, bacterial and fungal infections;

Contraindications

- Increased individual sensitivity;
- Pregnancy, lactation;
- Children younger than 1 years old;

- Acute renal failure.

With caution

- chronic renal failure (used no more frequently than 2 times a week).

Posology and Administration

Polyoxidonium[®] route of administration: intranasal, sublingual.

Dose regimen, route of administration, the need and the frequency of subsequent therapy are chosen by the physician depending on the disease severity and the age of the patient.

Posology and administration in adults and children older than 12 years.

The drug is administered intranasal or in the sublingual area for 7-10 days at a daily dose of 6 mg:

Intranasal	In the sublingual region
1 spray into each nostril - 5 times a day	2 sprays - 5 times a day

Posology and administration in children aged 1 to 12 years.

The drug is administered intranasal or in the sublingual area for 7-10 days at a daily dose of 0.15 mg/kg:

Age	Intranasal	In the sublingual region
Aged 1 to 2 years	1 spray into each nostril - 1 time a day	1 spray - 2 times a day
Aged 2 to 5 years	1 spray into each nostril - 2 times a day	2 sprays - 2 times a day
Aged 5 to 8 years	1 spray into each nostril - 3 times a day	2 sprays - 3 times a day
Aged 8 to 12 years	2 sprays into each nostril - 2 times a day	4 sprays - 2 times a day

Side effects:

- An allergic reaction may develop in case of increased individual sensitivity to the product components.
- Possible body temperature elevation.

Overdose

No cases of overdose are recorded.

Interaction with other drugs

No drug–drug interactions have been identified.

Special warnings

If an allergic reaction is developed, immediately discontinue the use of Polyoxidonium® and consult a physician.

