5.8 Criteria for diagnosis

Acute respiratory viral infection (ARVI) is an acute, local (in most cases) respiratory tract infection presenting with catarrhal inflammation of the upper respiratory tract and proceeding with fever, runny nose, sneezing, cough, sore throat, a violation of the general condition of different manifestations.

The patient or parents (legal representatives) may complain of acute rhinitis and / or cough and / or conjunctival hyperemia (catarrhal conjunctivitis) in combination with symptoms of rhinitis, pharyngitis. The disease usually begins acutely, often accompanied by an increase in body temperature to subfebrile values (37.5 °C — 38.0 °C). Febrile fever is more typical for influenza, adenovirus infection, and enterovirus infections. Elevated temperature in 82% of patients is reduced by the 2-3rd day of the disease; longer (up to 5-7 days) febrile is maintained during influenza and adenovirus infection [7]. An increase of fever intensity during the disease period, or appearance of severe intoxication symptoms may indicate the accession of a bacterial infection. Repeated raise of temperature after a short-term improvement often related to development of acute otitis media following the long-lasting runny nose.

Nasopharyngitis is characterized by complaints of nasal congestion, discharge from the nasal passages, nasopharynx discomfort: burning, tingling, dryness, often accumulation of mucous discharge, which in children, flowing down the posterior pharyngeal wall, can cause a productive cough. When inflammation spreads to the mucosa of auditory tubes (Eustachitis), clicking, noise and ear pain may occur, and a sense of hearing may decrease. Clinical course of nasopharyngitis has the following age features: in infants - fever, discharge from the nasal passages, sometimes - anxiety, difficulty in feeding and falling asleep. In older children, the typical manifestations are rhinitis symptoms (peak on day 3, duration up to 6-7 days), in 1 / 3-1 / 2 patients - sneezing and / or cough (peak on day 1, average duration - 6-8 days), rarely - headache (20% in the 1st and 15% - up to the 4th day) [8].

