8.1 Inclusion criteria

A patient shall meet the following inclusion criteria:

1. Patients of both sexes aged 1 to 12 years inclusive.
2. Diagnosis of ARVI [ICD-10 code: J00 - Acute nasopharyngitis (runny nose), J02 - Acute pharyngitis, J02.9 - Unspecified acute pharyngitis, Acute laryngitis and tracheitis - J04, J04.0 - Acute laryngitis, J04.1 - Acute tracheitis, J04.2 - Acute laryngitis, Acute upper respiratory tract infections of multiple and unspecified localization - J06, J06.0 - Acute laryngopharyngitis, J06.9 - Acute upper respiratory tract infection, unspecified] confirmed by physician's examination: axillary temperature ≥ 37.0 °C (measured at the moment of physical examination) and Symptom Assessment Scale total score ≥ 5 points, not less than 3 of which should be related to ENT-organs and upper respiratory tract affection (accord. the Symptom Assessment Scale [Appendix 1]).
3. Not more than 24 hours from the onset of ARVI manifestations.
4. Signing an Informed Consent Form by one of the parents/adoptive parent of the child and the child him/herself (if aged ≥ 10 years);

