9.2 Diagnostic Scales and Patient's Diary

During the study, the patient's condition and the therapy efficacy will be evaluated using the following parameters: 1) "Symptom Assessment Scale" (Appendix 1) - completed by the physician, 2) IMOS scale completed by the physician (Appendix 2) and also by the parent / adoptive parent (Appendix 3).

Symptom Assessment Scale completion will be conducted on Visit 0, Visit 1, Visit 2 and Visit 3. Also, on Day 5 of therapy, in the patient's diary the Symptom Assessment Scale shall be filled in; this procedure will be performed by the parent/adoptive parent. IMOS scale completion (Appendix 3) and assessment of the ongoing therapy efficacy by the patient's parent/adoptive patient (excellent, good, satisfactory, not efficient) will be held on Visit 3.

In addition, parents / adoptive parents of patients will be given a diary to record the patient's body temperature (twice a day: morning and evening), the time of taking the study product / placebo, the time and amount of taking antipyretic (paracetamol) and other drugs and their dosage and method of taking patients' complaints.

The diary and the diagnostic scales completed by the physician are the primary documentation; upon completion of the examination by the patients, they should be collected and kept together with the patient's medical record. When using electronic diaries, the data downloaded from them will be stored in the Investigator's file.

When conducting Visit 1 procedures, the Investigator must train the parents / adoptive parent to fill out a diary. At each visit, the Investigator must verify the correctness and timeliness of filling the diary with the patient's parent / adoptive parent.

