All adverse events that occurred during the study (start, duration, ending, description, intensity, outcome), as well as measures for their relief, are recorded in the CRF. In the event of serious adverse events (SAEs), it is necessary to inform representatives of the study sponsor / representatives of the contract study organization within 24 hours.

Any adverse medical event that meets the definition of AE, which, moreover, at any dose, will be considered a serious AE (SAE):

- leads to death;
- poses a threat to life;
- leads to persistent or significant disability or incapacity;
- leads to inpatient hospitalization or extension of current hospitalization;
- represents a congenital anomaly or birth defect;

- any adverse medical event that may not immediately threaten the life and lead to death or hospitalization, but from a medical and scientific point of view may pose a threat to the patient or require the intervention to prevent any of the above outcomes.

These events are usually considered serious.

Attention: the term "life-threatening" refers to an adverse event in which there is a risk of patient's death due to this reaction at the time of adverse event. This does not apply to any event that would hypothetically lead to death, if it would be more serious.

Analysis of safety parameters is based on the following data:

- frequency of occurrence and development of adverse events (AEs) recorded, according to the data of spontaneous patients' reports, clinically significant changes in vital signs (HR, RR) and clinically significant deviations of laboratory test indicators and instrumental methods of examination from baseline values;
- overall assessment of the tolerability of study products by the patient's parent/ adoptive parent and the Investigator.

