On Visit 0 (Screening), Visit 1 (Day 1), Visit 2 (Day 3), Visit 3 (Day 8 ± 1), the following basic vital signs are measured: HR, RR, body temperature. Clinically significant changes on visits - Visit 1 (Day 1), Visit 2 (Day 3), Visit 3 (Day 8) absent on Visit 0 (Screening) may be regarded as AE, depending on the clinical situation, at the discretion of the study physician; in this case, they are documented in the patient's medical record and in the CRF.

ECG

12-lead ECG can be performed on Visit 0 (Screening), only if there is a suspicion of cardiovascular pathology.

11.2 Requirements to reports, procedures for recording adverse events and intercurrent diseases and requirements for notification of regulatory authorities

When studying the efficacy of Polyoxidonium®, nasal and sublingual spray, 6 mg / ml (NPO Petrovax Pharm, Russia), a mandatory requirement is the concomitant assessment of the safety and tolerability of the studied doses in patients with a specific disease for whom this drug is being developed (in this case for children aged 1 to 12 years).

The presence and severity of adverse events after taking the investigated drugs will be assessed according to the complaints of patients and / or their parents / adoptive parents, physical examination data and the results of laboratory and instrumental examinations. At the same time, during observation of patients, known AEs related to the use of drugs with the active substance of Azoximer bromide and described in the current instructions for use of the drug Polyoxidonium® (section 5.2) will be especially taken into account.

The Investigator is responsible for notifying the Sponsor of any event that seems unusual, even if this event may be considered as an unexpected benefit to the patient.

All AEs that will occur with the patient after the first dose of the investigational drugs in the indicated dose will be registered.

With the development of any adverse events, the Investigator must record the case in the patient's medical record and fill in the appropriate pages of the CRF, assess the feasibility of continued patient's study participation. Adverse events will be registered from the time of the first use of the drug until the completion of the study.

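### Body temperature, a named side effect, is missing from the section 11 safety data list, and the home diary temperatures have no planned safety analysis

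*Combined protocol and SAP*

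**What the plan says.** Section 5.2.1 lists two side effects of the product. One is allergic reaction; the other is "Possible body temperature elevation". Section 11.2 says that known reactions to the active substance, as described in section 5.2, will receive particular attention.

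The protocol describes temperature as safety data in different ways:

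- Section 11, in its list of the data behind the safety analysis, has "clinically significant changes in vital signs (HR, RR) and clinically significant deviations of laboratory test indicators". Temperature is not named.
- Section 11.1, under major vital signs, says "the following basic vital signs are measured: HR, RR, body temperature" at Visits 0 to 3. The Appendix 5 footnote defines vital signs the same way.
- Section 11.1 then says that clinically significant changes "absent on Visit 0 (Screening) may be regarded as AE, depending on the clinical situation, at the discretion of the study physician".
- Section 11.2 has the general rule: "All AEs that will occur with the patient after the first dose of the investigational drugs in the indicated dose will be registered".
- Section 12.4 plans descriptive statistics for vital signs, with change from baseline, at each visit.

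Entry under section 8.1 requires "axillary temperature ≥ 37.0 °C (measured at the moment of physical examination"). Parents receive "a diary to record the patient's body temperature (twice a day: morning and evening"), and section 10 names these diary temperatures as efficacy data.

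**The concern.** The product has a temperature rise among its named side effects, and the trial's primary endpoint is fever duration. Temperature is therefore the variable on which benefit and a known harm are hardest to separate. The plan uses the detailed record, the diary, for benefit only. For harm it relies on visit readings and on physician judgement, and the list that defines the safety data omits the variable.

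A late rise also matters clinically by the protocol's own account. Section 5.8 says: "Repeated raise of temperature after a short-term improvement often related to development of acute otitis media". If such rises differed between arms, the randomised placebo comparison could show it, but only if they were tabulated.

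**Working it through.** No formula applies; the check sets the sections side by side.

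**1. Is temperature in the safety data?** Section 11 brackets vital signs as HR and RR. Section 11.1 and Appendix 5 include temperature. Section 9.1.6 leans towards section 11: it ties HR and RR measurement to the safety assessment, then deals with temperature under its own subheading without that statement. The sections conflict, and the text does not say which governs.

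**2. How does a rise become an adverse event?** For the physical examination, section 11.1 says that significant changes absent at Visit 0 are treated as adverse events. For vital signs it says only that they may be, at the physician's discretion. Entry temperature is at least 37.0 °C, and the end of fever is defined as 36.9 °C or below on two consecutive measurements, so every child enters above the end-of-fever threshold. The plan does not say whether a return of fever after normalisation, or a rise above the entry value, counts as absent at Visit 0. It gives no size, timing or recurrence criterion.

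**3. What temperature data reach a planned safety summary?** Vital signs are measured at Visits 0, 1, 2 and 3. The Visit 0 and Visit 1 readings precede the first dose. That leaves Visit 2 (Day 3) and Visit 3 (Day 8 ± 1): two clinic readings per child. Section 12.2 mentions change from baseline at Visit 3 only; section 12.4 covers each visit. No section assigns the twice-daily diary readings to a safety table.

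**4. What else could show a rise between visits?**

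| Planned output | What it would miss |
|---|---|
| Temperature normalisation on Day 5 (two consecutive readings of 36.9 °C or below) | A recurrence after Day 5, or one that has settled by then |
| Paracetamol intakes over the whole study | A rise above 37.0 °C but below 38.5 °C, the level at which sections 5.5 and 7.4 allow the drug |
| Dropouts needing antibacterials; withdrawals by reason | A rise that leads to neither |
| General adverse event reporting | A rise that the family does not report or the physician does not judge to be an event |

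The first two rows, and the antibacterial dropout count, are efficacy criteria. Section 12.2 analyses efficacy in the per-protocol population, not the safety population.

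**5. Does the primary endpoint cover a later rise?** The end of fever is two consecutive readings of 36.9 °C or below. The text does not say whether the first or the last such pair is meant, and gives no rule for a later rise. The primary endpoint therefore cannot be relied on to show recurrence.

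**The case against.** The strongest reply is that the bracket in section 11 is a drafting slip. Temperature is a vital sign in section 11.1 and Appendix 5, and sections 12.2 and 12.4 summarise vital signs by arm. The physician observes the child for an hour after the first dose, the investigator checks the diary at Visits 2 and 3, families are told to report new symptoms, and adverse events are taken through Visit 4. A complication such as otitis media would itself be an adverse event. All of this stands, and it limits the point.

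It also rules out three stronger readings that a reader might infer.

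- *That the adverse event rule cannot register a temperature rise.* Not supported. The rule concerns clinically significant changes, so a rise over the child's own Visit 0 value, or a return of fever, can be recorded. The general rule in section 11.2 is a second route.
- *That every child is febrile at Visit 0.* Not exact. Entry needs one reading of 37.0 °C or more; the protocol's fever is above 37.0 °C on two measurements.
- *That a rise would be invisible in the results.* Not supported. The outputs in the table above would show some of them, by arm.

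The reply does not supply a recording criterion or a safety use for the diary. Those gaps remain.

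**Conclusion.** The point holds in a limited form. Section 11 omits a named side effect from its safety data and conflicts with section 11.1 and Appendix 5. Recording a rise is discretionary, under a test that is hard to apply at these entry temperatures. The diary has no planned safety analysis, so a low-grade rise or a recurrence between visits may not be systematically captured.

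The size cannot be put as a number of missed events: the documents give no frequency for the side effect or for recurrence. What can be said is that planned temperature summaries for safety after the first dose rest on two clinic readings, while a twice-daily record exists. This assumes that no separate document assigns the diary to safety; section 12 says that the final methods will be set out in more detail elsewhere.

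A reader might also conclude that any increase over the pre-dose reading should count as an adverse event. The documents do not support going that far: such a rule would register the ordinary swings of an acute febrile illness.

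**What to change.** 1. Reconcile section 11 with section 11.1 and Appendix 5 by listing body temperature among the vital signs in the safety data.
2. In section 12.4, add a by-arm table and listing in the safety population, from the existing diary, showing:
   - children whose temperature again meets the protocol's own fever definition (above 37.0 °C on two measurements) after the declared end of fever;
   - the highest diary temperature after the first dose against the last value before it.

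The table should state that it takes the first qualifying pair of normal readings as the end of fever. If the last pair were used, no recurrence could appear.

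The cost is a wording change and a little more analysis. No visit, measurement or treatment rule changes. Some disease-related rebounds will be listed in both arms; the placebo group is there to put them in context.

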11.1 Methods and terms of analysis safety parameters recording

The presence of adverse events is assessed according to the patients' complaints, as well as according to the physical examination and the results of laboratory and instrumental examination. Investigators are responsible for identifying, providing necessary medical care, documenting and reporting cases that fall within the definition of AE and SLEEP.

For safety assessment, the following laboratory parameters are determined according to the schedule of Visits (Visit 0 (Screening), Visit 3 (Day 8 ± 1)):

- Clinical blood test;
- Common urine analysis.

Laboratory deviations

Any clinically significant abnormalities in the clinical blood count, clinical urine analysis will be evaluated by the Investigator. In case of significant deviations of laboratory parameters on Visit 3 (day 8 ± 1) in comparison with the initial parameters at Visit 0 (screening), it is necessary to conduct additional laboratory monitoring before normalizing or determining the cause of the deviation.

Any additional laboratory control is carried out by the Investigator's decision. Any clinically significant laboratory deviation shall be documented as AE in the patient's medical record and in the CRF unless the deviation is due to laboratory error; in this case, a corresponding note shall be made in the primary documents.

General medical history and anamnesis morbi

General information about the medical history and anamnesis morbi is collected on the screening visit and includes:

- date of disease onset;
- previous and concurrent diseases, and surgery in the previous 6 months prior to the study inclusion;
- concomitant therapy (drug products, other treatments) and products used for 6 months prior to the study inclusion;
- smoking, alcohol and narcotic drug abuse.

Physical examination

A general physical examination is conducted on Visit 0 (Screening), Visit 1 (Day 1), Visit 2 (Day 3), Visit 3 (Day 8 ± 1). Clinically significant changes on visits - Visit 1 (Day 1), Visit 2 (Day 3), Visit 3 (Day 8 ± 1), absent on Visit 0 (Screening) are regarded and documented as AE in the patient's medical record and in the CRF.

Major vital signs

On Visit 0 (Screening), Visit 1 (Day 1), Visit 2 (Day 3), Visit 3 (Day 8 ± 1), the following basic vital signs are measured: HR, RR, body temperature. Clinically significant changes on visits - Visit 1 (Day 1), Visit 2 (Day 3), Visit 3 (Day 8) absent on Visit 0 (Screening) may be regarded as AE, depending on the clinical situation, at the discretion of the study physician; in this case, they are documented in the patient's medical record and in the CRF.

ECG

12-lead ECG can be performed on Visit 0 (Screening), only if there is a suspicion of cardiovascular pathology.

11.2 Requirements to reports, procedures for recording adverse events and intercurrent diseases and requirements for notification of regulatory authorities

When studying the efficacy of Polyoxidonium®, nasal and sublingual spray, 6 mg / ml (NPO Petrovax Pharm, Russia), a mandatory requirement is the concomitant assessment of the safety and tolerability of the studied doses in patients with a specific disease for whom this drug is being developed (in this case for children aged 1 to 12 years).

The presence and severity of adverse events after taking the investigated drugs will be assessed according to the complaints of patients and / or their parents / adoptive parents, physical examination data and the results of laboratory and instrumental examinations. At the same time, during observation of patients, known AEs related to the use of drugs with the active substance of Azoximer bromide and described in the current instructions for use of the drug Polyoxidonium® (section 5.2) will be especially taken into account.

The Investigator is responsible for notifying the Sponsor of any event that seems unusual, even if this event may be considered as an unexpected benefit to the patient.

All AEs that will occur with the patient after the first dose of the investigational drugs in the indicated dose will be registered.

With the development of any adverse events, the Investigator must record the case in the patient's medical record and fill in the appropriate pages of the CRF, assess the feasibility of continued patient's study participation. Adverse events will be registered from the time of the first use of the drug until the completion of the study.

With the development of SAE, the patient stops taking the drug, but is under the supervision of the Investigator until the resolution or stabilization of the resulting condition. With the development of AE, the patient is under the supervision of the Investigator until the resolution or stabilization of the resulting state.

Adverse events registration

In the occurrence of a serious adverse event (SAE), you must fill in a special notification form (Appendix 4) and report it to ClinPharmInvest LLC and NPO Petrovax Pharm LLC, Russia, namely: send within 24 hours the corresponding completed form by fax or e-mail to the **Qualified Person Responsible for Pharmacovigilance (QPPV) or his/her Deputy**, NPO Petrovax Pharm LLC, Russia.

Qualified Person Responsible for Pharmacovigilance: [name]

[contact] [name]

[contact]

[contact]

e-mail: [contact]

Deputy QPPV: [name]

Email: [contact]

[contact] [name]

Responsible for the collection of information on SAEs for and on behalf of the organization conducting the study:

[contact]; [contact]

e-mail: [contact]

Full name: [name]

All SAEs must be traced until they are resolved or stabilized.

Any subsequent information relating to previously reportable SAEs will be reported according to the same procedures and within the same deadlines. The scope of information for registration of SAE is presented in Appendix 4.

Non-serious adverse events are registered in a working order and provided to the Sponsor at the end of the study (or earlier, if necessary). All non-serious AEs will be reported to the Sponsor at the end of the study in the form of a study report.

The Principal Investigator and the contract study organization, ClinPharmInvest LLC, shall be responsible for the control of reports to the Local Ethics Committee of all cases of AEs/SAEs..

Reporting to the Regulatory Authority about all cases of AE/SAE is in the responsibility of the company - Sponsor NPO Petrovax Pharm LLC, Russia.

Pregnancy

If a female patient is detected as pregnant, she cannot be included in the study. All cases of pregnancy identified during the course of a clinical trial are recorded by the Investigator in the primary documentation of the participants in the clinical trial and the corresponding "Pregnancy Report Form".

A report on the detected case of pregnancy against the background of the use of the study product / placebo is also reported to the Sponsor, LEC/NEC within 24 hours from the moment of receiving information about this event.

Any patient who becomes pregnant during this clinical trial will be excluded from the study.

In the event that a participant of a study / sexual partner of a participant in a study that has occurred during the study or within 3 weeks after it, the participant in the study is obliged to inform the study physician.

Further, with the consent of the pregnant participant/partner of the participant, the study physician will monitor the course of pregnancy until the moment of delivery.

Any complication of pregnancy or a planned termination of pregnancy for medical reasons should be recorded as a SAE. The following cases will meet the severity criteria in such a situation:

- report on the development of congenital anomalies or malformations in a child/fetus;
- report on fetal death;
- spontaneous abortion;
- reports on adverse events in the newborn classified as serious.

Such cases as abortion report without indicating information on the presence or absence of congenital malformations, reports on the drug effect on pregnancy without outcome data, or reports containing information on the normal outcome, are not subject to urgent reporting, since they do not contain an unambiguous indication of the presence of a suspected adverse reaction. However, these reports should be processed in the same way as other reports of adverse reactions to the drug.

